Protocol title: Comparison of Arm and Ankle Blood Pressure during Cesarean Delivery: A Blood Pressure Cuffs Pilot Study

NCT#: 2020H0502

IRB approval date: 14MAR2021

Comparison of Arm and Ankle Blood Pressure during Cesarean Delivery: A Blood Pressure Cuffs Pilot Study

BACKGROUND AND SIGNIFICANCE

A literature search found the incidence of hypotension after subarachnoid block (SAB) varied between 7.4% and 74.1%,^[1] while another recent publication discovered the incidence of hypotension to be 5.4%.^[2] There is a large variation of definitions used for intraoperative hypertension (IOH) in anesthesia literature. The relationship between these definitions and the incidence of IOH is depicted in Figure 1.^[3]

[figure not shown]

Figure 1. Incidences of hypotension after SAB and the definitions of hypotension

In the last three decades, numerous interventions have been studied and implemented into our daily practice, such as pre-loading versus co-loading, phenylephrine versus ephedrine, and phenylephrine infusion versus intermittent boluses. In addition, the effectiveness of left uterine displacement (LUD) to improve blood flow and pressure remains unclear. Also, there are issues to be addressed on this regard, including:

1. Poor placental perfusion from inadequate LUD due to the potential impact of supine hypotensive syndrome (SHS) secondary to aortocaval compression especially after SAB;
2. Shivering during cesarean delivery (CD) resulting in inaccurate BP measurements, the incidence of shivering during CD is reported to be 21.9%.^[4] It is unclear the impact of shivering during CD on blood pressure (BP) measurements;
3. Patient discomfort during BP measurements, calf > arm > ankle.^[5]

One study concluded there is poor correlation between arm and calf BP. They found calf BP was higher than arm BP, with an average difference in SBP of 18.3 ± 18.6 (95% CI: 14.0~22.6) before spinal anesthesia and

14.2 ± 21.0 (95% CI: 9.4~19.1) before incision/after spinal, and average difference in MAP of 4.8 ± 11.8 (95% CI: 2.1~7.6) before spinal anesthesia and 0.1 ± 13.6 (95% CI: 2.1~7.6) before incision/after spinal anesthesia.^[6] In contrast, another study of healthy non pregnant volunteers demonstrated insignificant differences in average SBP differences (22.4 [95% CI: -2.7~47.4]) and average MAP differences (3.7 [95% CI: -12.3~19.7]) among both ankles and arm.^[5] A recent study reported the incidence of maternal systolic hypotension at 5 min post-SAB to be 16.7% in the LUD group and 53.3% in the non-LUD group.^[7] However, imaging findings have not existed in MRI studies with low risk parturients but possible at high-risk for SHS^[8, 9] who may benefit from LUD and other aggressive preventive measures to avoid undesired consequences.^[10, 11]

Nevertheless, none of studies have discussed issues related to SAB, LUD, SHS, and differences of between arm and ankle BP comprehensively. There are also the issues of sidedness of ankle BP measurements, as LUD tilts the body to the left side which may contribute to differences between arm and ankle BP.

Specific Aims

- To validate the effectiveness of LUD after SAB with simultaneous measurements of BP on the arm and left ankle during surgery in patients undergoing cesarean delivery (CD) at The Ohio State University Wexner Medical Center
- To determine whether ankle BP correlates more accurately than arm SBP with the incidence of nausea/vomiting and category II or III fetal heart tracing and bradycardia after SAB and LUD under no shivering conditions in patients undergoing C-Section at The Ohio State University Wexner Medical Center
- To determine the impact of body mass index and antepartum estimation of newborn weight on SHS^[12] after the SAB

MATERIALS AND METHODS

Location:

The OSUWMC Labor & Delivery

Null Hypothesis:

The magnitude of the differences in arm and ankle SBP is consistent before and after spinal anesthesia.

Study design:

A single center prospective self-control study.

Study population: eligibility will be determined by the inclusion/exclusion criteria specified below. After eligibility has been confirmed, data from up to 100 subjects will be enrolled.

Inclusion Criteria:

- a. Age ≥ 18 years old

- b. Women undergoing cesarean delivery at The Ohio State University Wexner Medical Center under spinal anesthesia
- c. American Society of Anesthesiologists Physical Status I-III
- d. Body mass index during pregnancy $\geq 35 \text{ kg/m}^2$
- e. Able to consent in English language
- f. Singleton pregnancy

Exclusion criteria:

- a. Women undergoing elective cesarean delivery at The Ohio State University Wexner Medical Center under anesthesia other than spinal anesthesia (i.e. general and/or epidural anesthesia)
- b. Prisoners

Sample size:

For this pilot study, a sample size of 100 patients will offer valuable information on clinical outcomes for future randomized clinical trials on blood pressure monitoring in patients undergoing C-Section under SAB.

Outcomes:

- Primary outcome: difference of SBP measured between arm and ankle during elective CD before and after (pre-incision) SAB
- Secondary outcomes: incidence of nausea, vomiting and shivering, estimated blood lost, blood transfusion (e.g. packed red blood cells units), category II or III fetal heart tracing, fetal bradycardia, APGAR at 1 min and 5 min, neonatal intensive care unit admission rate, SBP differences between arm and ankle before and after LUD performed in before surgery and anesthesia (baseline), after spinal anesthesia, after the fetus delivered

Statistics:

Maternal and newborn parameters (e.g. age, weight, height, body mass index, gravida and parity, gestational age, newborn weight, and high-risk obstetrics factors), clinical parameters (e.g. degree of tilt, compression, and incidence of shivering) will be summarized using descriptive statistics (mean/standard deviation, median/IQR, frequencies/proportions) based on data characteristics.

In addition, descriptive statistics will be used to summarize differences between arm and ankle blood pressures taken at different time-points. Multivariable linear regression models will be used to evaluate associations between changes in the magnitude of difference in SBP/MAP measures from different time-points taking clinical factors such as degree of tilt, compression, shivering, and baby weight into account.

A Bland-Altman plot for arm and left ankle paired SBP taken during CD under spinal anesthesia will be created to identify bias and estimate 95% agreement limits.^[6, 14, 15, 16] SBP and MAP will be obtained at 6 data collection points preoperatively/pre-spinal with and without LUD, after SAB in supine position and LUD, and right after the fetus delivery in LUD, and supine after the delivery.

Data collection:

1. Demographic data: age, weight, height, gestational age, newborn weight, HROB factors, locations of placenta, past medical history (i.e. cardiovascular disease), and circumferences of arm and ankle for BP measurements
2. Systolic and Mean Arterial Blood Pressure: measured concomitantly at different time points on arm (standard of care) and left ankle (research purposes)
 - a. Pre-spinal: supine and after LUD with 15° tilt ^[17] (≥ 1 measurement as required by standard of care)
 - b. Post-spinal: supine and after LUD (≥ 1 measurement as required by standard of care)
 - c. After delivery: supine and after LUD (≥ 1 measurement as required by standard of care)
 - d. Incidence of intraoperative shivering, nausea/vomiting, category II or III fetal heart tracing, fetal Bradycardia, intubation, and neonatal intensive care unit admission after cesarean delivery
3. Newborn's clinical variables documented in the medical records as standard of care (e.g. heart rate and APGARs at 1 min and 5 min)
4. Cord blood pH (if performed by standard of care)

Study procedures:

- Cuff size: large BP cuffs will be the default size for both arm and ankle measurements, but can be changed as clinically indicated based on circumferences of limbs
- Cuff location: BP cuffs will be placed on the contralateral arm to the main peripheral IV following standard procedures. Left ankle cuff will be placed underneath intermittent pneumatic compression cuffs
- Spinal anesthesia will be administered following standard of care anesthesia management for patients undergoing cesarean delivery at The OSUWMC
- Hypotension avoidance strategies (e.g. phenylephrine infusion beginning at 50 mcg/kg/min) will be implemented per anesthesia provider clinical criteria
- Fetal monitoring will be implemented as required by standard of care practices in patients undergoing cesarean delivery at The OSUWMC
- Ankle blood pressure monitor screen will be covered. Thus, anesthesia providers will not be able to make any clinical decisions based on ankle blood pressures but arm blood pressure (standard) instead.

ANTICIPATED IMPACT

Placement of BP cuffs on left ankle during CD after SAB may become standard of care and provide more comfort than the current standard of care. The difference between SBP or MAP in patients positioned supine and after LUD before SAB may become a simple method to identify parturients at high-risk for SHS and prevent perioperative complications.

ADVERSE EVENTS OR UNANTICIPATED PROBLEMS INVOLVING RISK TO PARTICIPANTS OR OTHERS

Any patient privacy/confidentiality breach will be recorded and reported following our Institutional Review Board (IRB) guidelines.

RISKS

No research-related invasive monitoring techniques/procedures are required in our study. Blood pressure values will be collected during surgery by IRB approved researchers. Demographics and past medical history will be collected from electronic medical records as documented per **standard of care** by health care providers. Breach of confidentiality is the only recognized risk. To protect patient privacy, a limited data set will be created. During data collection, team members will remove any patient identifiers except for the codified database which will be stored on a password secured OSUWMC server. Moreover, any paper documents will be locked in our research's office (Department of Anesthesiology, Clinical Research Office, The OSUWMC). All data will only be available to the PI and designated research personnel.

PRIVACY/CONFIDENTIALITY ISSUES

All reasonable efforts will be made to keep a patient's protected health information (PHI) private and confidential. There will be limited access to medical records and codification of all records. Federal privacy guidelines will be followed when using or sharing PHI.

Data will be stored electronically in our Department encrypted L-drive which is password protected and available only to IRB approved research personnel working on this study. The Ohio State University PCs have been compatible to the latest institutional Information System security policies. Computer databases will be maintained on password protected OSUWMC PCs at the Clinical research Office, Department of Anesthesiology ([name]).

All study staff have completed required institutional education regarding patient confidentiality, Good Clinical Practices, Human Subjects Protection and Responsible Conduct of research trainings as required by Office of Responsible Research Practices (ORRP).

RECORD RETENTION

Research Records will be retained for a period of six (6) years after the submission of the final report and close-out procedures on the research project for which the Research Records were prepared. The retention of the original Research Records shall be the responsibility of the Principal Investigator.

REFERENCES

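### Arm cuff side follows the IV and the plan does not ask for it to be recorded, so the supine-versus-LUD contrasts may carry an arm-height artefact if LUD is done by tilting the table

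*Combined protocol and SAP*

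**What the plan says.** - **Cuff placement.** Study procedures states that "BP cuffs will be placed on the contralateral arm to the main peripheral IV following standard procedures". The ankle cuff is always on the left ankle. Arm side can therefore differ between patients while ankle side cannot.
- **LUD contrasts.** The secondary outcomes include "SBP differences between arm and ankle before and after LUD performed in before surgery and anesthesia (baseline", repeated after spinal anesthesia and after delivery. Statistics adds that "SBP and MAP will be obtained at 6 data collection points", which matches three phases in two positions (3 × 2 = 6). Aim 1 (effectiveness of LUD) rests on the same comparison.
- **Intended use.** Anticipated Impact says: "The difference between SBP or MAP in patients positioned supine and after LUD before SAB may become a simple method to identify parturients" at high risk of supine hypotensive syndrome.
- **Sidedness.** The Background recognises the issue for the ankle: "There are also the issues of sidedness of ankle BP measurements, as LUD tilts the body to the left side". It does not raise it for the arm.
- **Data and model.** For the limbs, Data collection item 1 lists "circumferences of arm and ankle for BP measurements", not cuff side. The regression is to be fitted "taking clinical factors such as degree of tilt, compression, shivering, and baby weight into account".
- **LUD method.** Data collection item 2a gives a 15° tilt for the pre-spinal reading and cites reference 17, whose title concerns a table tilt. Reference 13 concerns a wedge. No section says which is used, and items 2b and 2c give no angle.
- **Primary outcome.** Neither the primary outcome nor the null hypothesis names a position.

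**The concern.** A cuff above heart level reads low and one below it reads high. If the whole table tilts to the left and the arms go with it, a right-arm cuff moves up and a left-arm cuff moves down. The left ankle moves down in every patient. The ankle-minus-arm SBP difference then changes between supine and LUD for purely geometric reasons, and the arm part of that change has opposite signs on the two sides.

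Adjusting for degree of tilt does not remove it. A single tilt coefficient averages two slopes of opposite sign, weighted by an unrecorded mix of arm sides.

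At stake are the LUD secondary outcome, Aim 1 and the hoped-for screening use. The last is a per-patient use, so a balanced mix of arms would not help: each patient keeps her own offset. An arm-only supine-versus-LUD difference would carry the same gap between sides; an ankle-only difference would not.

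**Working it through.** The plan gives no figure for this effect, and the sample size of 100 comes with no SD or precision target, so there is no stated number to reproduce.

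**Inputs**
- From the documents: 15° tilt (Data collection, item 2a); n = 100; arm-calf SBP difference SDs of 18.6 before and 21.0 after spinal (Background, from the cited arm-calf study).
- Assumed, not in the documents: whole-table tilt with the arms moving; 0.779 mmHg per cm of height; arm cuff a = 15-30 cm from midline, with 50 cm as an extreme; left ankle k = 5-15 cm from midline; equal distances on the two sides.

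**Step 1: pressure per cm of lateral distance.** c = 0.779 × sin 15° = 0.2016 mmHg/cm.

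**Step 2: shift in ankle minus arm, LUD minus supine.** With L the true LUD effect:
- right-arm cuff: L + (a + k)c
- left-arm cuff: L − (a − k)c

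**Step 3: gap between arm sides.** The difference is 2ac; the ankle term drops out.
- a = 15: 2 × 15 × 0.2016 = 6.0 mmHg
- a = 30: 2 × 30 × 0.2016 = 12.1 mmHg
- a = 50: 2 × 50 × 0.2016 = 20.2 mmHg
- at 5° rather than 15°, a = 15: 2 × 15 × 0.779 × sin 5° = 2.0 mmHg
- wedge with level arms: about 0

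**Step 4: mean offset when a share p of cuffs is on the left arm.** The mean offset is c[k − a(2p − 1)], which has two separate parts.

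| Share on left arm | Arm-side part, −ac(2p − 1), a = 15-50 cm |
|---|---|
| 20% | +1.8 to +6.0 |
| 50% | 0 |
| 80% | −1.8 to −6.0 |

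The left-ankle part is kc = +1.0 to +3.0 mmHg whatever the arm side.

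**Step 5: what recording arm side can recover.** The equal-weight average of the two sides is L + kc. The arm part cancels and the ankle part stays. If all cuffs were on one side there would be no contrast to use, and the offset would be constant: (a + k)c = +4.0 to +13.1 if all right, −(a − k)c = −9.1 to 0.0 if all left (a = 15-50, k = 5-15).

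**Step 6: precision of the gap at n = 100.** The SD of change is taken as √(18.6² + 21.0² − 2r × 18.6 × 21.0) = 23.5 to 15.5 for assumed r = 0.3 to 0.7. The 95% half-width is t(0.975, 98) × SD × √(1/n₁ + 1/n₂):
- 50/50: 6.1-9.3 mmHg
- 80/20: 7.7-11.7 mmHg

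These SDs describe arm-calf differences before and after spinal, not ankle-arm differences between supine and LUD. The half-widths are indicative only and could err either way.

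**Step 7: primary outcome.** Two positions before and two after SAB give 2 × 2 = 4 pairings, of which 2 are same-position. In those two, a static arm-side offset appears at both times and cancels, provided arm and angle do not change.

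**The case against.** The size rests on geometry that the documents do not contain. If LUD is done with a wedge and the arms stay level, there is almost nothing to correct. The 20 mmHg figure needs a cuff 50 cm from midline. At an even arm split the arm part of the mean offset is zero. All of this stands, and it makes the point conditional.

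Absence from the data list is also weak evidence. That list omits degree of tilt as well, yet Statistics says that "clinical parameters (e.g. degree of tilt, compression, and incidence of shivering) will be summarized using descriptive statistics". The regression factors are an open list, so arm side might be recorded and used. But nothing in the plan asks for it, and it needs to be noted when the reading is taken.

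The remedy is limited too: it leaves the left-ankle offset, gives imprecise by-side estimates, and cannot adjust if nearly all cuffs are on one side. That also stands, and the limits belong in the report.

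A reader might infer that the LUD results will be biased, or that the primary outcome is compromised. The documents support neither. They do not fix the LUD method or give the arm mix, so even the direction of a mean offset is unknown. The primary is protected by same-position pairing, which an analyst would probably choose anyway. The unnamed position is missing detail, not a demonstrated error.

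**Conclusion.** The point holds as a modest, conditional one about the supine-versus-LUD contrasts. Cuff arm side varies by design, is not requested, and cannot be replaced by degree of tilt as a covariate. If the table is tilted 15° and the arms move with it, the gap between arm sides is about 6-12 mmHg for cuffs 15-30 cm from midline. The arm-side part of the mean offset runs from 0 at an even split to 1.8-6.0 mmHg in size at 20% or 80% left (cuffs 15-50 cm from midline). The separate left-ankle offset of about +1 to +3 mmHg is not an arm-side effect and should not be counted as one. Confidence is medium: the gap in the plan is plain, but its size depends on assumed geometry and an unknown arm mix.

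**What to change.** 1. **Data collection.** Add cuff arm side and LUD method (table tilt or wedge), and record the degree of tilt at each LUD reading.
2. **Statistics.** Report the LUD contrasts by arm side, with the equal-weight average of the two sides, as descriptive results. State that the average still contains the left-ankle offset. If nearly all cuffs are on one side, say that no adjustment is possible and give the constant offset as a limitation.
3. **Outcomes (minor clarification).** Define the primary as the within-patient change in signed (ankle minus arm) SBP difference at the same named position before and after SAB. This cancels a static arm-side offset and keeps the LUD effect out of the SAB comparison.

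The cost is two tick-boxes, a tilt value per LUD reading, one table and one sentence. No extra pressure readings are needed. The drawback is imprecision: at n = 100 the by-side results describe the data and will not settle whether an artefact is present.

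### The only listed outcome for left uterine displacement is an arm-ankle SBP difference, which captures only the part of its effect that differs between limbs

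*Combined protocol and SAP*

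**What the plan says.** The first item under Specific Aims is "To validate the effectiveness of LUD after SAB with simultaneous measurements of BP on the arm and left ankle during surgery". Background and Significance puts the open question as whether LUD improves blood flow and pressure.

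The Outcomes section mentions LUD once, at the end of the secondary outcomes: "SBP differences between arm and ankle before and after LUD performed", at baseline, after spinal anesthesia and after delivery. The primary outcome is "difference of SBP measured between arm and ankle during elective CD before and after (pre-incision) SAB", and the Null Hypothesis is "The magnitude of the differences in arm and ankle SBP is consistent before and after spinal anesthesia". Both compare the arm-ankle gap across the block, not across LUD. The other secondary outcomes (nausea, fetal tracing, Apgar and so on) are listed once per woman or newborn, not as supine-versus-LUD contrasts. Incidence of hypotension is not listed.

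In the Statistics section, "descriptive statistics will be used to summarize differences between arm and ankle blood pressures taken at different time-points", the regression concerns "changes in the magnitude of difference in SBP/MAP measures from different time-points", and the Bland-Altman plot pairs arm with left ankle SBP.

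Data collection provides for SBP and MAP at the arm and left ankle, supine and after LUD, at all three stages.

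**The concern.** An aim about whether LUD works calls for an outcome that moves when LUD raises pressure. The listed outcome is a difference between limbs, so it moves only when the two limbs respond unequally. If LUD relieved compression and lifted arm and ankle pressure together, the listed outcome would on average stay where it was. A change in it would show an unequal limb response, which is not the same as benefit. As written, Aim 1 has no listed outcome that measures the pressure response itself.

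The missing quantity could be derived later from the stored readings. It would then be chosen after the data were seen, from 2 limbs x 2 pressures x 3 stages = 12 candidates.

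**Working it through.** **Plan's own figure.** The only number is the sample size of 100. It comes with no alpha, power, effect size or SD, so there is no calculation to reproduce.

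**Algebra.** Let A be arm SBP and K ankle SBP, and let D = A - K. Then

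D(LUD) - D(supine) = [A(LUD) - A(supine)] - [K(LUD) - K(supine)] = arm change - ankle change.

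A rise c common to both limbs contributes c - c = 0. This needs no assumption about SDs or correlations. Illustrative cases:

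| Arm change (mmHg) | Ankle change (mmHg) | Listed contrast (mmHg) |
|---|---|---|
| +5 | +5 | 0 |
| +10 | +10 | 0 |
| +15 | +15 | 0 |
| +10 | +20 | -10 |
| 0 | +5 | -5 |
| -5 | 0 | -5 |

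The first three rows cannot be told apart. Nor can the last two, although in one the ankle rises and in the other the arm falls.

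**How much is lost.** If the ankle change is k times the arm change, the contrast is (1 - k) times the arm change: 0 at k = 1, a quarter of it in size at k = 1.25, and all of it in size at k = 2. The documents give no value or range for k.

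**What 100 women would show.** Inputs:
- SD of the limb difference: 21.0 mmHg, from the arm-calf study cited in Background and Significance (after spinal), used as a proxy for arm-ankle.
- Assumed: correlation r of 0.3 to 0.7 between the supine and LUD gaps, and a two-sided alpha of 0.05. The plan states neither.

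SD of the change in the gap = 21.0 x sqrt(2(1 - r)) = 24.8 mmHg at r = 0.3, 21.0 at r = 0.5 and 16.3 at r = 0.7. The 95% half-width is 1.96 x SD / sqrt(100), which gives 4.9, 4.1 and 3.2 mmHg.

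Rejection probability under a paired normal approximation:
- Common rise of 5, 10 or 15 mmHg with no extra ankle rise: 5%, equal to alpha.
- Extra ankle rise of 2 mmHg: 13% to 23%.
- Extra ankle rise of 5 mmHg: 52% to 87%.
- Extra ankle rise of 10 mmHg: 98% to more than 99%.

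For the arm change alone, assuming its SD is 10 to 25 mmHg, the 95% half-width is 1.96 x 10 / 10 = 2.0 to 1.96 x 25 / 10 = 4.9 mmHg. Power is 52% to more than 99% for a 5 mmHg rise, and 98% to more than 99% for 10 mmHg.

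A simulation of 20,000 trials checked this. It used a common rise averaging 10 mmHg (SD 8), a limb offset with SD 14.8, and reading-to-reading SDs of 8 (arm) and 12.6 (ankle). The SD of the gap is then sqrt(14.8^2 + 8^2 + 12.6^2) = 21.0. The arm-ankle contrast rejected in 5.0% of trials and the arm change in 100%.

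**The case against.** **The gap may be the intended marker.** Background and Significance names aortocaval compression as the worry, so a larger response at the ankle than at the arm is plausible, and the listed contrast has reasonable power for one of 5 mmHg or more. This stands as a reason to keep the gap as an outcome. The protocol does not state that rationale, however, and it notes that tilt itself may contribute to arm-ankle differences. A change in the gap is therefore not a direct reading of benefit.

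**The gap removes shared disturbances.** Providers act on arm pressure and may give vasopressors, and pressure also drifts with time since the block. A simultaneous limb difference removes whatever affects both limbs equally; a within-limb change does not. This stands and limits what the added outcome can claim.

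**The regression may already cover it.** The sentence on "changes in the magnitude of difference in SBP/MAP measures from different time-points" does not name arm versus ankle and could be stretched to a within-limb change. That is an ambiguity. It does not clearly define the missing outcome.

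**Two stronger readings are tempting.** A reader might infer that most of the LUD effect is invisible, by turning the cited hypotension rates of 16.7% with LUD and 53.3% without into a shift of 0.083 + 0.966 = 1.05 SD and supposing that the ankle responds only slightly more than the arm. The documents do not support this. The rates compare groups in another study, no hypotension definition or SBP SD is given for it, and nothing fixes the relative ankle response. A reader might also take the Anticipated Impact sentence, "The difference between SBP or MAP in patients positioned supine and after LUD before SAB", as the intended conclusion of Aim 1. It names no limb, concerns the period before the block, and offers a future way to identify women at risk. Aim 1 concerns the period after the block.

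**Conclusion.** The point holds as an outcome that does not match its aim. The cancellation is exact: an equal rise in both limbs has expected value 0 on the listed contrast, whatever its size. The contrast is not blind to LUD, since it retains any response that differs between limbs. The share of the effect lost cannot be given from the documents. The rejection probabilities rest on an arm-calf SD and on an assumed alpha, correlations and within-limb SDs; the algebra does not.

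A reader might infer that the plan will declare LUD ineffective when it works. The documents do not go that far: they state no LUD hypothesis, test or decision rule. The false null is a risk of interpretation. Because this is a pilot and the paired readings are to be collected, no data are lost and the gap can be closed in the text. It is worth closing before analysis, since otherwise the first-listed aim lacks a prespecified measure of the pressure response.

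**What to change.** In Outcomes and Statistics, add as the lead Aim 1 outcome the within-woman change in SBP from supine to LUD after SAB, for arm and left ankle separately, each with mean, SD and 95% CI. Make MAP, and the pre-spinal and post-delivery stages, supportive. State the order of positions at each stage: after delivery, Statistics lists LUD before supine while Data collection lists supine first.

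Keep the arm-ankle difference before and after LUD as a separate outcome that answers a narrower question: does LUD move the ankle more than the arm? Say in the regression sentence which difference is modelled.

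The cost is a sentence or two in each section and no new measurement. There are a few more estimates, but only two lead ones. Because the within-limb change also carries vasopressor use and time since block, report it descriptively and not as proof of an LUD effect. Its SD would also help in planning the future randomized trials that the Sample size section mentions.

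### The single Bland-Altman plot under spinal anesthesia would mix two positions, two phases and repeated pairs per patient; the plan should separate them or model them

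*Combined protocol and SAP*

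**What the plan says.** The Statistics section plans the agreement analysis in one sentence: "A Bland-Altman plot for arm and left ankle paired SBP taken during CD under spinal anesthesia will be created to identify bias", together with 95% limits of agreement. No confidence interval is mentioned for either. The next sentence lists six collection points: two before the block, then "after SAB in supine position and LUD, and right after the fetus delivery in LUD, and supine after the delivery". Under Data collection, items 2a to 2c give the same grid (three phases, each supine and after left uterine displacement, LUD) and allow one or more readings.

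Three other statements bear on the point:

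- The end of Background and Significance notes that the leftward tilt of LUD may itself alter the arm-ankle difference.
- The primary outcome is the "difference of SBP measured between arm and ankle during elective CD before and after (pre-incision) SAB". A secondary outcome is "SBP differences between arm and ankle before and after LUD performed in before surgery and anesthesia (baseline), after spinal anesthesia, after the fetus delivered".
- Outside the plot, "descriptive statistics will be used to summarize differences between arm and ankle blood pressures taken at different time-points".

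The Sample size section gives 100 patients with no precision target; Study population says up to 100.

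**The concern.** Four of the six scheduled points fall under spinal anesthesia, so one plot of all such pairs holds at least four points per patient, and more for patients with extra readings. The text gives no rule for selecting pairs, for separating positions or phases, or for handling repeats.

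Two things follow if the text is applied as written. First, the bias is an average over supine and LUD, before and after delivery, weighted by however many readings each contributes. If position matters, as the protocol suspects, that average describes neither position. It also does not match the primary outcome, which is pre-incision. Second, pairs from one patient are likely to be correlated. An analyst who adds a confidence interval to the bias or limits and counts every pair as independent would overstate the precision. The sample size rationale is that "a sample size of 100 patients will offer valuable information on clinical outcomes for future randomized clinical trials on blood pressure monitoring", so the bias and its precision are figures that later trials may use.

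**Working it through.** **Inputs.** From the protocol: 100 patients; two positions in each of two phases under spinal, so m = 4 pairs (m = 2 if pre-incision only); SD of the systolic difference 21.0 mmHg, from the cited arm-calf study after spinal (Background and Significance), standing in for arm-ankle. Assumed, because the documents give neither: within-patient correlation r = 0.3, 0.5, 0.7, and the shift D between supine and LUD.

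**Check of the plan's figures.** The plan states no precision to reproduce. The cited intervals are coherent with their SDs: half-widths (22.6 − 14.0)/2 = 4.30 and (19.1 − 9.4)/2 = 4.85 give n = (1.96 × 18.6/4.30)² = 71.9 and (1.96 × 21.0/4.85)² = 72.0.

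**1. Bias.** With equal counts the pooled bias is the midpoint of the two positions, so it is off by D/2 for each: 2.5, 5 or 10 mmHg for D = 5, 10 or 20. With unequal counts, if a fraction p of patients gives twice as many pairs as the rest, their weight rises from p to 2p/(1 + p). The difference peaks at 0.17 (p = 0.41), so the bias moves by at most 0.17 times the difference in bias between the two groups of patients.

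**2. Limits of agreement.** Expected pooled variance with 400 pairs = [21²(400 − 1 − 3r) + 400(D/2)²]/399. The half-width is 1.96 times its root, against 1.96 × 21 = 41.2 within one position.

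| D | pooled half-width, r = 0.3 to 0.7 |
|---|---|
| 0 | 41.1 |
| 5 | 41.3 to 41.4 |
| 10 | 42.2 to 42.3 |
| 20 | 45.5 to 45.6 |

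**3. Confidence interval for the bias (D = 0).** The half-width that treats pairs as independent is 1.96 × 21/√(100m). The correct one multiplies this by √(1 + (m − 1)r).

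| m | independent | r = 0.3 | r = 0.5 | r = 0.7 | coverage of nominal 95% |
|---|---|---|---|---|---|
| 4 | ±2.06 | ±2.84 | ±3.25 | ±3.62 | 84%, 78%, 73% |
| 2 | ±2.91 | ±3.32 | ±3.56 | ±3.80 | 91%, 89%, 87% |

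Simulation with four pairs agreed.

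**4. Confidence interval for a limit (m = 4, D = 0).** Independent: 1.96 × 21 × √(1/400 + 1.96²/(2 × 399)) = ±3.5. Correct: 1.96 × 21 × √[(1 + 3r)/400 + (1.96²/4)v], with v = [2 × 99(1 + 3r)² + 2 × 300(1 − r)²]/399², which gives ±4.3, ±5.0 and ±5.8.

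**5. Precision of the alternatives, 100 patients.** One pair per patient per point: bias 1.984 × 21/√100 = ±4.2; limits 1.984 × 21 × √(1/100 + 1.96²/198) = ±7.1. Repeated-measures model on four single pairs with similar variance at each point: limits 1.96 × 21 × √[1/100 + (1.96²/4)w], with w = [2(1 + 3r)²/99 + 18(1 − r)²/297]/16, which gives ±5.2, ±5.6 and ±6.1.

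**The case against.** The strongest reply is that the plan promises only a bias and 95% limits, and step 2 shows that pooling barely moves the limits. This stands. A reader might infer that every interval from the pooled plot is too narrow; the documents do not support that. The only intervals planned are the limits, and mixing positions widens them if anything. Even a naive confidence interval for the bias is not too narrow in every case: with D = 10 or 20 it is conservative when r is below about 0.02 or 0.08.

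A second reply is that position and phase results are planned elsewhere. This also largely stands. The primary outcome, the LUD secondary outcome and the time-point summaries supply the means, so it would be wrong to infer that the before-and-after-spinal comparison is lost. Limits per point could even be derived from those summaries, provided that one pair per patient enters each, which is not stated.

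Third, the wording may name a method rather than a single figure, or may mean pre-incision pairs only. Either is possible. In the second case there are two scheduled pairs, the understatement is smaller, and the D/2 error between positions remains. Neither reading says which pairs are plotted.

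Fourth, no size for D is given. The cited arm-calf difference moved by 18.3 − 14.2 = 4.1 mmHg, and a reader might take that as D. It is a change across the block at the calf, not a contrast between supine and LUD, and is not used here.

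A reader might also extend the point to the planned regression: "Multivariable linear regression models will be used to evaluate associations between changes in the magnitude of difference in SBP/MAP measures from different time-points". One change score per patient per model raises no clustering problem, and nothing in the text shows another intention.

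**Conclusion.** The point holds for the agreement analysis only. As written, the plot blends two positions and two phases, with repeated and possibly unequal numbers of pairs per patient. The bias is then off by D/2 for each position under equal counts, with D unknown. The limits themselves are close to right or slightly wide.

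The understatement of uncertainty is conditional: it affects confidence intervals that the plan does not promise, under positive within-patient correlation. At r = 0.3 to 0.7 a correct interval for the bias is about 1.4 to 1.8 times the naive one with four pairs, and 1.1 to 1.3 times with two. These figures assume 100 patients, an arm-calf SD of 21.0 and equal correlation between all pairs.

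In a pilot where the plot carries no test or decision rule, this is of minor to moderate weight. It is still worth correcting now, because the remedy is cheap.

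**What to change.** State in Statistics which pairs enter the agreement analysis. Either:

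- make one Bland-Altman plot per time point and position, with one pre-specified pair per patient (for example the first reading in that position), including the pre-incision points that match the primary outcome; or
- if pairs are pooled, use a repeated-measures Bland-Altman model with position and phase effects and a patient random effect, report bias and limits for each point, and check that the variance is similar across points.

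In both cases, base any confidence interval on patients and not on pairs.

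The cost is a few sentences, plus a few more plots or one mixed model. No extra patients or measurements are needed. Reported intervals will be wider than naive pooled ones: with the first option about ±4.2 mmHg for the bias and ±7.1 mmHg for the limits at each point, if all 100 patients contribute and the SD is 21.0, and wider still if fewer are enrolled.
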